5.1.3. Route and mode of administration

For Part A, DF2755A will be administered orally, at T0h (around 8:00 a.m), in sitting position, in fasting conditions, with 200 ml of tap water.

For Part B, repeated administrations will be performed at T0h (around 8:00a.m) and at T12h (around 8:00p.m). For each subject, these administrations will be performed with an authorised window of ± 15 minutes.

Treatments will be administered under the supervision of the Investigator, in the Clinical Pharmacology Unit EUROFINS OPTIMED.

The actual time of drug administration will be documented in the source documents and reported in individual eCRF.

5.2. Accountability procedures for the investigational product(s)

5.2.1. Responsibilities

The Investigator, the pharmacist or other personnel allowed to store and dispense IMP will be responsible for ensuring that the Investigational Treatment used in the study is securely maintained as specified by the Sponsor and in accordance with the applicable regulatory requirements.

The IMP will be dispensed in accordance with the Investigator's prescription and it is the Investigator's responsibility to ensure that an accurate record of Investigational Product issued and returned is maintained.

5.2.2. Accountability

Details of the quantities of each medication dispensed will be entered onto the accountability form. At the end of the study, the amount of each product retained (if required) in the Clinical Unit and the remaining amount (if any), will be returned to the Sponsor or destroyed after a final reconciliation (if agreed with the Sponsor). A copy of the form will then be sent to the Sponsor, together with any remaining medication (if agreed) (see section 5.2.3).

Specific procedures for the IMP preparation, dispensation, storage and destruction when required will be detailed in the “pharmacy manual for study OP099516.DOM”. This document will be supplied by the pharmacist of Eurofins Optimed and approved by the sponsor, apart from the study protocol.

5.2.3. Return and /or destruction of IMP

Investigational medicinal product reconciliation must be performed at the site by the Investigator (or the pharmacist) and the monitoring team using the appropriate form countersigned by the Investigator (or the pharmacist) and the monitoring team. Test materials (including investigational products and placebo) remaining at the end of the study will be returned to the Sponsor or their representative, or destroyed on behalf of the Sponsor after a final reconciliation of investigational medicinal product.

In case of destruction, a written authorization for destruction will be given by the clinical trial team once the investigational medicinal product reconciliation is achieved. This destruction will be performed by the pharmacist or delegated person and a certificate of destruction will be provided.

5.3. Medication(s)/treatment(s) permitted and no permitted before and/or during the trial

No concomitant therapy (prescribed or non-prescribed drug included OTC) will be allowed during the study, except paracetamol (maximum 500mg per administration, total daily dose maximum 2g). However, in case of intercurrent illness or emergency, the investigator is allowed to use any needed medication.

This must be done with a particular attention to the available pharmacological knowledge of the given medication and possible interaction(s) with the study drug. In case of intake of any concomitant medication during the study, the following information must be noted in the relevant section of the eCRF:

- Name of the treatment and its form,
- Reasons for prescription,
- Date and time of start,
- Route of administration,
- Daily dose,
- Duration of treatment.

The decision to withdraw the subject may be made by mutual agreement between the Investigator and the Sponsor.

5.4. Procedures of monitoring subject compliance

Administration will be performed under medical supervision. A mouth control will be performed immediately after the administration.

6. ASSESSMENT OF PHARMACOKINETIC

Derivation of PK parameters will be carried out by PhinC Development using WinNonlin® Professional software (Version Phoenix 6.4 – Pharsight Corporation – Mountain View, California – USA). A non-compartmental analysis approach will be performed.

The statistical analysis will be carried out by PhinC development using the SAS® package (release 9.4).

In each part of the study, a first interim PK analysis with nominal time points will be run after completion of each dose level. After database lock, a final analysis will be run with actual time points. For the interim analysis, no formal statistics will be presented.

After completion of the bioanalytical part of the study, an electronic copy of the quality checked and validated data will be provided to PhinC Development.

6.1. Pharmacokinetic endpoints

For the calculation of the PK parameters and characteristics the following rules will be applied:

- All the plasma concentrations validated by the bioanalytical laboratory and provided to the pharmacokineticist will be used for the PK analysis.
- The actual blood sampling time points related to the preceding administration will be used if available. Otherwise, nominal blood sampling times will be taken into account.
- At time points in the lag-time between time zero and the first concentration equal or above the limit of quantification (LOQ), concentrations below LOQ will be set to zero (0). Concentrations below LOQ between 2 concentrations equal or above LOQ will be considered as missing data. Trailing concentrations below LOQ will not be used in calculations.
- For plasma concentration above the upper limit of quantification (ULOQ) and reported as above the limit of quantification (ALQ) in the final plasma concentration tables, ALQ will be replaced by the first measurement for the PK analysis.
- Not reported concentration (NR) will be excluded from the PK analysis.
- If pre-dose concentration is less than or equal to 5% of C_{max} value in a PK profile, the subject's data can be included in all PK measurements and calculations without any adjustments. If the pre-dose value is greater than 5% of C_{max} , the subject will be dropped from all statistical evaluations (applicable only at the predose on day 1).

According to the study part and the day of PK assessment, the following PK parameters of DF2577Y bound and unbound (or related metabolites) will be derived from DF2577Y (or related metabolites) plasma concentrations for each subject on Day 1 (SAD and MAD parts) and on Day 14 (MAD part):

$C_{max}/C_{ss, max}$ The observed maximum plasma concentration of DF 2577Y (or metabolites) measured in a subject after dosing identified by inspection of the plasma drug concentration *versus* (vs.) time data by Phoenix WinNonlin.

$C_{ss, min}$ The observed plasma concentration of DF 2577Y (or metabolites) measured in a subject at 12 h post-dose just before the second daily dosing *versus* (vs.) time data by Phoenix WinNonlin (Day 14 in MAD part only).

$C_{ss, av}$ The average concentration at steady-state defined as the ratio $AUC_{0-t/t}$ (Day 14 in MAD part only).

$t_{max}/t_{ss, max}$ The time at which C_{max} was apparent, identified by inspection of the plasma drug concentration vs. time data by Phoenix WinNonlin.

t_{lag} The time before occurrence of the first quantifiable plasma concentration will also be obtained directly from the concentration-time data; it is the time point immediately prior to the first quantifiable plasma concentration.

λz The terminal plasma elimination rate-constant will be estimated from log-linear regression analysis of the terminal phase of the plasma concentration *vs.* time profile (SAD part and MAD part Day 14 only). For the slope of the terminal elimination phase to be accepted as reliable, the following criteria will be imposed:

- a coefficient $r^2 \geq 0.90$,
- a minimum of 3 data points, including the last measured data point and excluding C_{max} , are available for the regression.

If these 2 criteria could not be met, the slope of the terminal elimination phase will be considered as not calculable and all the parameters derived from this value ($AUC_{0-\infty}$, $t_{1/2}$, ...) will be reported as not calculable (NC).

t_{1/2} $t_{1/2}$ will be calculated according to the following equation: $t_{1/2} = \ln 2 / \lambda z$ (SAD part and MAD part Day 14 only).

AUC_{0-t} The area under the concentration *vs.* time curve over the dosing interval will be calculated using a linear trapezoidal method (*i.e.* from time zero (pre-dose) to 12 h post-dose in MAD part only).

AUC₀₋₂₄ The area under the concentration *vs.* time curve from time zero (pre-dose) to 24 h post-dose will be calculated using a linear trapezoidal method (SAD part only).

AUC_{0-t} The area under the concentration *vs.* time curve from time zero (pre-dose) to the time of last quantifiable concentration will be calculated using a linear trapezoidal method.

AUC_{0-∞} The area under the serum drug concentration *vs.* time curve from time zero to infinity: $[AUC_{0-\infty} = AUC_{0-t} + (C_t/ke)]$, where C_t = the observed concentration of drug for the last sample on the PK profile in which drug was detected, and ke as defined above. The percentage of extrapolation of $AUC_{0-\infty}$ should normally not exceed 20% to consider the value as reliable (SAD part only).

fu Fraction of unbound in plasma

Cl/F The apparent volume of the central compartment cleared of drug per unit time will be estimated using the formula (DF 2577Y only in SAD part only).

$$Cl/F = \text{Dose} / AUC_{0-\infty}$$

Vd/F The apparent volume of distribution based on the terminal elimination phase. The estimate does not account for the bioavailability (F, as a fraction of 1) and is therefore nominally divided by this value when drug is given via extravascular routes (DF 2577Y only in SAD part only).

$$Vd/F = Cl/F / ke$$

PTF The peak trough fluctuation will be calculated on Day 14 as the following ratio:

$$[(C_{ss, max} - C_{ss, trough})/C_{ss, av}]$$

where $C_{ss, trough}$ is the pre-dose concentration measured on the day of assessment.

In the MAD part, accumulation ratios will be calculated for C_{max} and AUC_{0-t} between Day 14 and Day 1 for each compound.

Parent to metabolite ratios will be calculated for C_{max} and all AUCs.

The following PK parameters of DF 2577Y (or related metabolites) will be derived from DF 2577Y (or related metabolites) urine concentrations for each:

Ae Amount of DF 2577Y (or related metabolites) measured in a given urine fraction:

$Ae = DF 2577Y$ (or related metabolites) concentration measured in the fraction \times Urinary volume of the fraction

fe Percentage of the dose excreted in the urine (DF 2577Y only) determined over various time intervals (24 h post-dose and t_{last} in SAD part; 12 and 24 h post-dose on Day 1 in MAD part).

Cl_R Renal clearance determined as the ratio Ae_{0-t}/AUC_{0-t} with $t = 24$ h post-dose and t_{last} in SAD part and $t = 12$ and 24 h post-dose on Day 1 in MAD part

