6.2. Specification of pharmacokinetic parameters

Part A:

The following pharmacokinetic parameters will be determined from DF2755Y (the acid form of DF2755A and for metabolites if any):

- C_{max} (ng/mL);
- t_{max} (h);
- λ_Z ;
- $t_{1/2}(h)$;
- AUC_{0-24} (h \times ng/mL);
- AUC_{0-t} (h \times ng/mL);
- $AUC_{0-\infty}$ (h \times ng/mL);
- fu
- V_Z/F (DF2577Y only);
- CL/F (DF2577Y only);
- Ae_{0-24} and AUC_{0-last} ;
- fe_{0-24} and fe_{0-last} ;
- CL_R ;
- Total amount in faeces;
- Parent:metabolite(s) ratio for C_{max} and AUCs..

Part B:

The following pharmacokinetic parameters will be determined from DF2577Y (the acid form of DF2755A and for metabolites if any):

Day 1

- C_{max} (ng/mL);
- t_{max} (h);
- t_{lag} (h);
- λ_Z ;
- $t_{1/2}$ (h);
- AUC_{0-12} (h \times ng/mL);
- Ae_{0-12} and Ae_{0-24} ;
- fu ;
- fe (%);
- CL_R : renal clearance;
- Parent:metabolite(s) ratio for C_{max} and AUCs.

Day 14

- $C_{ss,max}$ (ng/mL);
- $t_{ss,max}$ (h);
- t_{lag} (h); $C_{ss,min}$ (ng/mL): measured plasma concentration at the end of the dosing interval;
- λ_Z : terminal phase rate constant;
- $t_{1/2}$ (h): terminal half-life;
- AUC_{0-t} (h \times ng/mL);
- $C_{ss,av}$ (ng/mL);
- fu ;
- Ae_{0-last} ;
- Total amount in faeces;
- Parent:metabolite(s) ratio;
- Accumulation ratios for C_{max} and AUC_{0-12} .

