6.3. Methods and timing for assessing, recording, and analysing pharmacokinetic parameters

6.3.1. Collection, treatment and storage of blood samples

Blood sampling will be performed for DF 2755Y concentration measurements at the exact time-points with an authorised time-window described in the table below.

When ECG, vital signs and PK are required at the same time, this specific order will be followed: ECG first, then vital signs and blood sample for PK at the end.

Part A :

Day	Sampling time	Sample N°	Time window(min)
1	T0 (pre-dose)	P00	
	T0h30min	P01	+/-1
	T1h00	P02	+/-3
	T2h	P03	+/-3
	T3h	P04	+/-5
	T4h	P05	+/-5
	T5h	P06	+/-5
	T6h	P07	+/-5
	T7h	P08	+/-5
	T8h	P09	+/-5
	T9h	P10	+/-5
	T10h	P11	+/-5
	T12h	P12	+/-5
	T16h	P13	+/-5
2	T24h	P14	+/-15
	T36h	P15	+/-15
	T40h	P16	+/-15
3	T48h	P17	+/-15
	T60h	P18	+/-15
4	T72h	P19	+/-15

After the determinations of DF 2755Y in plasma samples during cohort 1 and according to results obtained, the blood sampling times and the collection periods could be reviewed to optimize the collection times with respect to the PK profile of DF 2755Y.

Part B :

Day	Sampling time	Sample N°	Time window(min)
1	T0 (pre-dose)	P00	
	T0h30min	P01	+/-1
	T1h00	P02	+/-3
	T2h	P03	+/-3
	T3h	P04	+/-5
	T4h	P05	+/-5
	T5h	P06	+/-5
	T6h	P07	+/-5
	T7h	P08	+/-5
	T8h	P09	+/-5
	T9h	P10	+/-5
	T10h	P11	+/-5
	T12h	P12	+/-5
	T16h	P13	+/-5
2	Pre-dose/T24h D1	P14	+/-15
5	T0 (pre-dose)/ T24h D4	P15	+/-15
	T _{Cmax} ¹	P16	+/-15
	T12h	P17	+/-15
	T _{Cmax} ¹	P18	+/-15
6	Pre-dose/T24h D5	P19	+/-15
10	T0 (pre-dose)/ T24h D9	P20	+/-15
	T _{Cmax} ¹	P21	+/-15
	T12h	P22	+/-15
	T _{Cmax} ¹	P23	+/-15
11	Pre-dose/T24h D10	P24	+/-15

Day	Sampling time	Sample N°	Time window(min)
14	T0 (pre-dose)/ T24h D13	P25	+/-15
	T0h30min	P26	+/-15
	T1h	P27	+/-15
	T2h	P28	+/-15
	T3h	P29	+/-15
	T4h	P30	+/-15
	T5h	P31	+/-15
	T6h	P32	+/-15
	T7h	P33	+/-15
	T8h	P34	+/-15
	T9h	P35	+/-15
	T10h	P36	+/-15
	T12h	P37	+/-15
	T16h	P38	+/-15
15	T24h D14	P39	+/-15
	T36h	P40	+/-15
	T40h	P41	+/-15
16	T48h	P42	+/-15
	T60h	P43	+/-15
17	T72h	P44	+/-15

¹This time (T_{Cmax}) will be determined thanks to part A results.

Blood handling procedures:

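### Part B Day 1 renal clearance over 24 h rests on a plasma AUC that the sampling cannot support; the 24-h fe has no stated denominator, and Sections 6.1 and 6.2 disagree on Day 1 half-life

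*Protocol*

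**What the plan says.** **Dosing.** Protocol Section 5.1.3: in Part B "repeated administrations will be performed at T0h (around 8:00a.m) and at T12h (around 8:00p.m").

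**Urinary parameters.** Section 6.1 defines fe as "Percentage of the dose excreted in the urine (DF 2577Y only) determined over various time intervals" and ClR as the ratio of urinary amount to AUC over the same window. For Part B, both are required at 12 "and 24 h post-dose on Day 1 in MAD part".

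**Plasma schedule.** In the Part B table of Section 6.3.1, Day 1 runs from pre-dose through T0h30, hourly from T1h to T10h, then T12h and T16h. The next sample is labelled "Pre-dose/T24h D1". Days 5 and 10 each have a sample at the expected peak after the evening dose; Day 1 has none.

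**AUC.** In Section 6.1 the area from time zero "to 24 h post-dose will be calculated using a linear trapezoidal method (SAD part only"). For Part B Day 1, Section 6.2 names AUC0-12 only, although it lists both Ae0-12 and Ae0-24.

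**Terminal slope and half-life.** Section 6.1 limits both to "SAD part and MAD part Day 14 only". It accepts a slope only with r² of at least 0.90 and "a minimum of 3 data points, including the last measured data point and excluding" Cmax. Section 6.2 nevertheless lists λz and t1/2 for Part B Day 1.

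**Urine.** Section 6.3.2 splits the Day 1 collection at T12h.

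**SAP.** Its pharmacokinetic text (Sections 3.3 and 4.3) deals with Part A, so it settles none of this.

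**The concern.** ClR over 0-24 h divides a complete urine collection by a plasma area whose second half rests on three concentrations: T12h, T16h and T24h. In the animal data the peak mostly comes 0.5-2 h after dosing, where nothing is drawn. A 12-h and a 24-h ClR would be reported side by side, and a difference between them caused only by sampling could be read as renal clearance changing with time.

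Two specification gaps sit next to this and do not depend on the missing samples:

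- **fe at 24 h.** Urine over 0-24 h contains drug from two doses. The plan does not say whether the percentage is of one dose or two, so two analysts could report values differing by a factor of two.
- **Day 1 half-life.** One analyst could follow 6.2 and report it; another could follow 6.1 and leave it out.

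ClR, λz and t1/2 are among the secondary endpoints in Section 3.1.2. fe is not listed there.

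**Working it through.** **1. Is the sampling gap real?** Part B pharmacokinetic samples counted from Section 6.3.1, for Days 1, 2, 5, 6, 10, 11, 14, 15, 16 and 17: 14 + 1 + 4 + 1 + 4 + 1 + 14 + 3 + 2 + 1 = 45. At 6 mL each this is 270 mL. Both figures match Section 8.2.3, so the table is complete and the gap between T12h and T16h is in the plan.

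**2. Model and inputs.** One compartment, first-order absorption, equal doses at 0 and 12 h. The true AUC is compared with the linear trapezoid at 0, 0.5, 1-10 (hourly), 12, 16 and 24 h. The documents give no human values. Assumed ranges: half-life 3-8 h (the summary range in Section 1.2.1.3) and tmax 0.5-4 h (0.5-2 h for most animal data; 4 h for the rat's second daily dose).

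**3. One case in full.** Half-life 4 h, tmax 1 h, concentrations scaled to dose/volume = 1.

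- Sampled values: T12h 0.133, T16h 0.597, T24h 0.149. The evening peak is 0.953.
- Trapezoid AUC12-24 = (0.133 + 0.597)/2 × 4 + (0.597 + 0.149)/2 × 8 = 4.44. True value 5.68, so 21.7% low.
- Trapezoid AUC0-24 = 4.95 + 4.44 = 9.39. True value 10.68, so 12.1% low.
- ClR0-24 is inflated by 10.68/9.39 − 1 = 13.8%.
- AUC0-12: trapezoid 4.95, true value 5.01, so 1.2% low.

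**4. Whole range (half-life 3-8 h, tmax 0.5-4 h).**

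| Evening absorption lag (assumed) | Error in AUC0-24 | Error in ClR0-24 |
|---|---|---|
| none | −16.8% to −4.4% | +4.6% to +20.1% |
| 1 h | −7.5% to +0.7% | −0.7% to +8.1% |
| 2 h | −2.3% to +8.2% | −7.6% to +2.3% |

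The error in AUC0-12 is −2.7% to −0.5% throughout. Widening the half-life to 1.5-13 h without lag gives ClR0-24 +4.4% to +37.6% and AUC0-12 −3.7% to −0.4%.

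**5. fe.** It uses urine and dose only, so plasma sampling is irrelevant. With constant renal clearance, the amount excreted is proportional to the true AUC. The two-dose amount over 0-24 h is 1.68 to 1.94 times the single-dose amount (no lag). Relative to a single-dose fe0-24, dividing by one dose reads 68-94% high. Dividing by two reads 3-16% low, because the second dose has only 12 h of collection.

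**6. Half-life.** A regression of three or more points that includes T24h has to cross the evening dose, since T16h and T24h alone are two points. Over half-life 1.5-13 h without lag, the best r² among declining fits was 0.51, against the required 0.90. With a 1 h or 2 h lag (half-life 3-8 h) the best was 0.39 and 0.29. Cut at T12h, a fit on T6h-T12h gives r² of at least 0.99. It recovers half-lives of 3-8 h within about 1% when tmax is 2 h or less. At tmax 4 h it overstates them: 5.2 h for a true 3 h, and 9.0 h for a true 8 h.

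**The case against.** **The direction of the ClR error is not fixed.** A reader might infer that the 24-h ClR is always too high. The documents do not support that. Section 1.2.1.3 reports a 4 h tmax in rats after the second daily dose, and T16h lies 4 h after the evening dose. With a 1-2 h evening lag the error shrinks and can turn negative. The dog data show a second peak at 1-2 h, so the animal evidence is mixed. This part of the objection stands: the value is unreliable, with a sign that depends on unknown human absorption.

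**fe is not affected by the missed peak.** Correct, since it uses no plasma. Near-doubling would occur only if an analyst divided by one dose, which the protocol does not instruct. What remains is the unstated denominator.

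**Half-life is a conflict between lists.** Also correct. A reader might infer that a misleading Day 1 half-life would be reported. Under the acceptance rule in 6.1, a fit including T24h would be recorded as not calculable. Section 6.1 also ties sampling times to the preceding dose, so the morning profile could be read as ending at T12h. Half-life still comes from Part A and from Day 14.

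**The sound value is already planned.** The protocol asks for ClR and fe at 12 h too, so nothing essential is lost. That limits the importance of the point, but the 24-h ClR is still a required output.

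**Conclusion.** The point holds as a minor defect in three parts.

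- **ClR at 24 h on Part B Day 1** is required, but the AUC it needs is not defined for Part B and not supported by the sampling. The error is about +5% to +20% under the no-lag model with half-life 3-8 h, and between about −8% and +8% with a 1-2 h evening lag. These sizes rest on a one-compartment model and animal-based ranges. The missing AUC definition and the sampling gap need no model.
- **fe at 24 h** has no stated denominator for a window holding two doses.
- **λz and t1/2 on Part B Day 1** are listed in 6.2 and excluded by 6.1. A slope fitted through T24h did not approach r² = 0.90 in any case tried.

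A reader might also infer a threat to dose escalation. ClR, fe and half-life appear in none of the rules in Section 3.5.4, and the primary endpoint is safety. Those rules do use a 24-h AUC; how it is obtained in Part B is a separate question, not assessed here.

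**What to change.** Protocol wording only; the SAP's pharmacokinetic text covers Part A and holds no Part B wording to change.

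- **Section 6.1:** restrict Part B Day 1 ClR and fe to 0-12 h. The 0-12 h urine interval and the dense 0-12 h plasma profile already exist, and that window contains a single dose.
- **Section 6.2:** delete λz and t1/2 from the Part B Day 1 list, state 0-12 h for fe and ClR, and report Part B half-life from Day 14, where sampling runs to T72h. Ae0-24 may stay as a descriptive amount, labelled as arising from two doses.

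Two alternatives are weaker. Dividing fe0-24 by both doses still reads 3-16% below a single-dose fe0-24. Cutting the slope at T12h overstates half-life if absorption is slow.

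The cost is the loss of a 24-h ClR and fe on Part B Day 1, with no added samples. Part B already needs a substantial amendment before it starts, which is a natural place for the change.

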6.2. Specification of pharmacokinetic parameters

Part A:

The following pharmacokinetic parameters will be determined from DF2755Y (the acid form of DF2755A and for metabolites if any):

- C_{max} (ng/mL);
- t_{max} (h);
- λ_Z ;
- $t_{1/2}(h)$;
- AUC_{0-24} (h \times ng/mL);
- AUC_{0-t} (h \times ng/mL);
- $AUC_{0-\infty}$ (h \times ng/mL);
- fu
- V_Z/F (DF2577Y only);
- CL/F (DF2577Y only);
- Ae_{0-24} and AUC_{0-last} ;
- fe_{0-24} and fe_{0-last} ;
- CL_R ;
- Total amount in faeces;
- Parent:metabolite(s) ratio for C_{max} and AUCs..

Part B:

The following pharmacokinetic parameters will be determined from DF2577Y (the acid form of DF2755A and for metabolites if any):

Day 1

- C_{max} (ng/mL);
- t_{max} (h);
- t_{lag} (h);
- λ_Z ;
- $t_{1/2}$ (h);
- AUC_{0-12} (h \times ng/mL);
- Ae_{0-12} and Ae_{0-24} ;
- fu ;
- fe (%);
- CL_R : renal clearance;
- Parent:metabolite(s) ratio for C_{max} and AUCs.

Day 14

- $C_{ss,max}$ (ng/mL);
- $t_{ss,max}$ (h);
- t_{lag} (h); $C_{ss,min}$ (ng/mL): measured plasma concentration at the end of the dosing interval;
- λ_Z : terminal phase rate constant;
- $t_{1/2}$ (h): terminal half-life;
- AUC_{0-t} (h \times ng/mL);
- $C_{ss,av}$ (ng/mL);
- fu ;
- Ae_{0-last} ;
- Total amount in faeces;
- Parent:metabolite(s) ratio;
- Accumulation ratios for C_{max} and AUC_{0-12} .

